3.3. Enrollment and Randomization

All patients who meet the clinical criteria listed above are eligible for SELECT 2 clinical enrollment. This includes both patients who are directly admitted to the study site and patients who are transferred from an outside hospital. The time of enrollment is the time when the informed consent is signed by the patient or their authorized legal representative. All patients or their surrogates will provide written informed consent. If a surrogate has provided informed consent, an attempt will be made to assess the competence of the patient again at day 1, discharge and at every follow-up in-person visit within 90 days of the procedure with the study team, if an in-person visit is feasible. If the patient is able to provide consent, informed written consent procedure will be reattempted, if an in-person visit is feasible.

3.4. Remote consent procedure:

A remote consent process to prevent delay in treatment is developed and included in the SELECT 2 protocol for participating sites that may want to implement such process. This remote consenting process will be utilized in cases when the patient himself/herself cannot provide an informed consent with the surrogate not being present on enrollment site. The key requirements of the process include provision of information regarding the study procedure in entirety followed by opportunity to ask questions and provision of contact information, and

receive completed ICF document with signature by the surrogate. An example of such process is described below. In places where only a legally authorize representative can consent for a research study, appropriate modifications will be made to the process described below.

1. Provision of information regarding the study procedure in entirety followed by opportunity to ask question:

1.1. This can be achieved by an audio call, a video call or a teleconferencing service. The identity of the surrogate should be confirmed by providing acceptable ID documents before providing patients' related identifiable information.

1.2. The surrogate should be encouraged to ask question. A contact number should be provided to the surrogate in case they have any further questions as they consenting process progress or later on.

2. Complete ICF document:

2.1. The treating center should transmit all pages of ICF document to the surrogate. All pages of ICF document, completed by the surrogate should be received by the treating center prior to enrollment and randomization of the patient.

2.2. Documents with incomplete information, i.e. absence of signature, absence of full legal name and absence of date and time of informed consent or missing pages of ICF document would not be considered adequate and must be received en-block and completed prior to enrollment and subsequent randomization into the study.

3. Confirmation of the identity:

The surrogate identity should be confirmed by providing acceptable ID documents before any identifiable information is shared and tthe completed informed consent form is transmitted.

4. Transmission of the information through a HIPAA compliant medium:

4.1. A HIPAA compliant secure medium should be used to transmit the data to the surrogate and receive the ICF back from the surrogate. These can include a secure institutional email with implemented HIPAA security features, Adobe Sign platform

approved for transmission of healthcare information or a fax number that is in possession of the intended recipient .

- 4.2. If the surrogate is present at the remote site, where the patient was first received before being transferred to the treatment center, the secured email from the Health Service Provider (HSP) at remote treatment site or fax machine under direct control and access of the HSP for the patient at remote treatment site can be used to transmit the information to and from the LAR.

5. Decreasing the burden of responsibilities from the surrogate as much as possible:

- 5.1. The study will ensure that the surrogate will receive assistance from the on-site ER physician/Nurse/research coordinators to decrease the burden of the consenting process including connecting with the surrogate, transferring the study information to the surrogate and returning the signed form to the study enrollment site. Use video conferencing if possible to establish the contact with the surrogate, provide ample opportunity to ask questions and answer all questions in detail. Request assistance from on-site healthcare personnel whenever available, provide protocol training to them beforehand and consider including them as the study personnel. Follow-up with another video call 15-20 minutes after the first contact to provide another opportunity to ask questions and assist in the process of signing and transmitting the ICF.

6. Documentation in the ICF

- 6.1. A complete documentation of the consenting process including the surrogate's name, relationship to the patient, method of transmission of ICF, mode of communication and verification of identity should be included in the ICF.

An example of such a procedure is provided below:

- Contact the appropriate surrogate by telephone/videoconferencing.
- Confirm the identity of the surrogate and how he/she is related to the patient.
- Discuss the study details, including procedures, study device and potential risks and benefits. Discuss the ICF and give instructions about where the surrogate needs to sign and date/time. The study will ensure that the surrogate will receive assistance from the on-site ER physician/Nurse/research coordinators to decrease the burden of the consenting process including connecting with the surrogate, transferring the study information to the surrogate and returning the signed form to the study enrollment site.
- Provide the ICF through a secure medium (Adobe Sign/email/fax).
- Provide the surrogate with a phone number to call you back in the event that she/he has questions. Follow-up with a phone/videoconferencing call after 15-20 minutes if they have any questions or need any help completing and returning the ICF.
- The surrogate should return the entire, signed and dated ICF back. The ICF is not valid and you cannot proceed with study enrollment unless all pages are received and appropriately filled out/signed/dated/timed.

After obtaining consent and ensuring all inclusion and exclusion criteria are met, randomization will be done in the emergency room prior to treatment using a web-based dynamic randomization system. Our randomization algorithm will be accessible to the study investigators and staff through a separate web page accessible only through the REDCAP database module. Covariate adaptive randomization will be used to balance the distribution of age (<60, 60-69, 70-79, 80-85 years old), presentation NIHSS (6-9, 10-15, 16-20, >20), center, clot location (M1, ICA), treatment time window (0-8, 9-16, 17-24 hours from onset to randomization time), CTP/MRP core volume (<50cc, 50-100cc, >100cc), presence or absence of target mismatch profile (mismatch ratio ≥ 1.8 & mismatch volume ≥ 15 cc) and hemisphere (right, left) between the two treatment groups.

The randomization algorithm we are going to implement is the algorithm developed by Pocock and Simon (1975)²⁷, i.e., minimization method. Through this algorithm, the assignment of a new patient to a treatment group is determined so as to minimize the differences between the groups in terms of these important key baseline variables. Unlike traditional stratified randomization, the minimization method works toward minimizing the total imbalance for all factors together instead of considering mutually exclusive subgroups, that is, we will not be creating these mutually exclusive subgroups during the randomization. Therefore, this approach is not restricted by the number of variables and the possible combinations of levels of balancing factors. Further details about Randomization can be found in Appendix A.

Eligible patients will be randomized into thrombectomy plus medical management vs medical management alone at a 1:1 ratio. The minimization algorithm is intended to balance the baseline characteristics between the two study arms, thrombectomy vs. medical management. The algorithm is not intended at the level of imaging profile subgroup. When a new patient is enrolled, the site will enter the stratification factor values into the dynamic randomization webpage and the treatment assignment will be determined immediately. An emergency 1-800 number will be provided if web-based randomization is not available due to exigent circumstances.

The assignment of the patients based on site assessment will be considered final for the primary analysis. A 1-800 number will be provided to the study investigators, where the case and imaging can be discussed with highly experienced vascular neurologists. A pre-specified secondary analysis based on core lab imaging assessment will be performed to address the cases where the core lab assessment differs from the site imaging assessment.

3.5. Endovascular Thrombectomy

The goal for femoral artery puncture will be within 45 minutes of randomization; femoral artery puncture must occur within 90 minutes of the completion of the qualifying imaging. Patients will be treated with thrombectomy devices (stent-retrievers) and/or suction (aspiration) thrombectomy systems currently cleared by the FDA for thrombus removal in patients experiencing an acute stroke within 24 hours of symptom onset following the published instructions for use for these devices. The devices which will be used are FDA-approved stent retrievers: the Trevo Retriever, the Solitaire Revascularization Device, EmboTrap Revascularization Device and Tigertriever Revascularization Device; and/or the aspiration devices approved by the FDA (e.g. MicroVention SOFIA Catheter, and the Penumbra thrombectomy system) permitted in the study. Please review Appendix C for a list of all approved devices. The choice of thrombectomy method, primary approach/technique, whether primary aspiration or primary stent-retriever with or without aspiration, will be left up to the interventionalist, with any of the FDA-approved devices approved in the study protocol or a combination of them (Appendix C). The study database will collect the thrombectomy method, and the devices used in the thrombectomy procedure.

Standard medical therapy, based on current AHA guidelines, will also be provided for all patients. Although any cleared neurothrombectomy device (Appendix C) can be used in the study, only the Solitaire Revascularization Device and Trevo Retriever are FDA-cleared to be indicated as a treatment in acute ischemic stroke patients to reduce their disability from the stroke. Individual investigators may use any of these devices or any combination of these devices to remove thrombus from the ICA, MCA M1 segment or, if needed, from M2 segments of the intracranial circulation. These are all approved anatomic locations for these devices. The use of thrombectomy devices should be performed in accordance with the indications for use and within the trial protocol. Any deviation from the on-label use of the device outside of the SELECT 2 protocol should be recorded in the appropriate case report form in detail. If there is severe stenosis of the common carotid artery or the proximal internal carotid artery,

investigators may also use devices for angioplasty or for stenting of the carotid artery as deemed appropriate. The use of adjuvant intra-arterial (IA) thrombolytic medication is not currently approved by the FDA for stroke treatment and cannot be used in SELECT 2.

Sites will use local protocols for femoral access, sedation, heparin infusion, monitoring, etc. Sites will perform a cervical injection of the involved carotid circulation as a baseline angiogram. At the conclusion of the procedure, a post-treatment angiogram as a cervical injection of the involved carotid circulation will also be obtained. Imaging will cover the full region of the normal circulation in AP and lateral projections at 2-3 films per second through the entire venous phase. All brain imaging from stroke onset through hospital discharge, including the MRI, CTP/MRP, and CT, as well as angiographic images obtained for the diagnostic and therapeutic portions of the procedure, will be transmitted to the core lab. The use of general anesthesia is left to the local investigators but discouraged by the study given the concerns of worse outcomes associated with that.

In cases of extracranial ICA occlusions, immediate stenting will be discouraged and delayed stenting (beyond 72 hours) will be preferred to reduce the risk of hemorrhagic transformation because of requirements of antiplatelet therapy/heparin to prevent re-occlusion.

3.6. Medical Management

Patients randomized to medical management alone will receive standard AHA guideline-directed medical therapy, which will include IV thrombolytic therapy available for use according to practice guidelines in patients presenting within the first 3 hours from last-seen-normal and meeting other FDA label criteria, or up to 4.5 hours from last-seen-normal and meeting other AHA guidelines. No procedures or tests required by the protocol will delay fastest possible delivery of thrombolytic therapy to potentially eligible subjects. The study database will collect the names of all thrombolytic drugs administered during the study, the route, the time of start of administration, and the dose administered. For non-thrombolysis treated patients, this will include aspirin 325 mg on day 1 followed by aspirin 81 mg or 325 mg

thereafter, which will be determined by treating physician, and standard deep venous thrombosis prevention therapy. Equivalent regimens of the aspirin will be allowed in countries where aforementioned doses are not commercially available. Intravenous anticoagulation and dual anti-platelet therapy will be discouraged without clear documented reasoning. Post-thrombolysis patients will be treated based on standard study site protocols for these patients.

3.7. Outcome Measures

3.7.1.1. Primary Outcome

The primary outcome #1 will be the distribution of mRS scores at 90 days. The primary outcome #2 will be the percentage of good outcome (mRS 0-2) at 90 days. The definition of favorable primary clinical outcomes is the patients' functional outcomes at 90 (+/- 15) days, measured by a modified Rankin scale (mRS) score of 0-2. The determination of mRS scores will be performed by certified raters unaware of the treatment arm or the baseline clinical and radiographic characteristics of the individual patient by in person interview or by telephone if in-person visit is not possible.

The shift in the modified Rankin Scale score is better equipped to capture potential improvement in the functional outcomes as compared to a binary (dichotomized) outcome with intervention. Since the study population is composed of acute stroke patients with significant ischemic changes (unfavorable imaging profiles), the potential shift across modified Rankin Scale Score categories, not only the functional independence, is of clinical significance. For details, a change of mRS score of 5 – completely bedridden to mRS score of 4 – ambulating with a wheelchair and to mRS score of 3 – ambulating with a cane is a successful outcome for thrombectomy. We will still have the dichotomized outcome as our second primary outcome.

3.7.1.2. Secondary Outcomes

Secondary outcome measures include: 1) safety as measured by the incidence of symptomatic intracranial hemorrhage (sICH) (SITS-MOST)²¹, neurological worsening (defined as a ≥ 4 -point

increase on the NIHSS score within 24 hours due to the stroke itself), mortality and groin (or arterial access site) hematomas, infections or any vascular injury caused by the endovascular procedure, 2) rates of recanalization (complete and partial) using the modified TICl system (score $\geq 2b$ defined as favorable reperfusion), 3) length of hospital stay, and 4) discharge location. 5) significant improvement of ≥ 8 points on NIHSS at 24 hours of presentation or an NIHSS of 0-1

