3.10. Assessment and Follow-up Visits

Baseline visit: The inclusion/exclusion page of the case report form must be completed to determine if the patient meets the eligibility requirements for the study. If the patient is eligible, then the consent form will be obtained by the patient or authorized representative.

24-hour visit (+/- 6 hours): The items listed for this visit in Table 2 should be performed between 18 and 30 hours from the time of the procedure.

Discharge visit: The items listed for this visit in Table 2 should be performed either on day 5/7 or the day of hospital discharge (whichever comes first).

30-day visit (+ / - 15 days): The items listed for this visit in Table 2 should be performed on day 30 (+/-15) days. The mRS score must be performed by an mRS certified evaluator who is blinded to treatment allocation. If possible, this visit should be completed in person. Telephone is allowed if the only option.

90-day visit (+ / - 15 days and preferably an in-person visit): The items listed for this visit in Table 2 should be performed on day 90 (+/- 15) days. The mRS score must be performed by an

mRS certified evaluator who is blinded to treatment allocation. The Neuro-QoL will also be completed on 90-day visit by an evaluator who is blinded to treatment allocation. If possible, this visit should be completed in person. Telephone is allowed if the only option.

365-day visit (+ / - 60 days): The mRS score must be performed by an mRS certified evaluator who is blinded to treatment allocation. The Neuro-QoL will also be completed on 360-day visit by an evaluator who is blinded to treatment allocation. Patients who were enrolled in the study at a date before the addition of the 365-day follow up visit, will be consented (remotely or in person) to complete the visit. The supplemental informed consent can be obtained verbally or in-written for patients who already provided their consents (or their LAR's consent) to participate in the study.

Neurological worsening: If clinical worsening (defined as a ≥ 4 point increase on the NIHSS score) occurs prior to discharge, a CT scan or MRI should be obtained as soon as possible. Neurological worsening is a reportable adverse event.

4. Sources of Materials

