Secondary analyses: Our secondary endpoint is the proportion of patients with mRS 0-2 at day 90 (indicating functional independence). The difference in the proportions of patients with mRS 0-2 between treatment arms will be assessed using logistic regression. We will adjust for the variables we used in adaptive randomization program in the logistic regression model. Other secondary endpoints include (1) the safety outcomes measured by the incidence of sICH, neurological worsening, mortality, groin hematomas, infections or vascular injury, (2) infarct volume, lesion growth, successful reperfusion, and recanalization rate, (3) length of hospital stay, and (4) discharge disposition. The exploratory analyses on secondary outcomes will include descriptive statistics (mean [\pm standard deviation, SD] or median and interquartile range for continuous variables and frequency [percentage] for discrete variables) and appropriate test for secondary outcome variables between two groups. For binary outcomes (e.g., sICH, neurological worsening, mortality, groin hematomas, infections or vascular injury, successful reperfusion, recanalization), Chi-square or Fisher's exact test where appropriate will be used to compare the incidence between two treatment groups for large core patients. We will also apply the logistic regression model on these outcomes after adjusting for the variables we used in adaptive randomization program. The adjusted odds ratio (OR), as well as 95% confidence interval will be reported. For the length of stay, mean \pm SD and median (Interquartile range) will be calculated for each group. For continuous variables (e.g., the length of stay and infarct volume), two sample t-test or Wilcoxon rank sum test as appropriate will be applied to compare them between two groups. For discharge disposition, frequency and percentage of each disposition will be reported and Chi-square test or Fisher's exact test where appropriate will be applied to compare its distribution between two groups.

Subgroup analyses: Subgroup analyses of the effect of thrombectomy on the primary and secondary endpoints will be performed. Subgroups will be defined based on the stratification variables, key demographic factors (such as race and ethnicity), thrombolysis vs. no thrombolysis, CTP vs. MRI selection, and witnessed vs. unwitnessed symptom onset, wake-up vs non-wake-up stroke, and TIC1 0-2a vs. TIC1 2b/3 results in the cath lab. An additional

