For endovascular patients with Extracranial Occlusions, we will conduct the two-step stopping rules for sICH after we enroll 20 patients in this group and then conduct monitoring after every 10 patients in this group (We expect 10% of patients will have isolated extracranial ICA occlusions, that is, among 280 endovascular patients, around 28 endovascular patients are with extracranial ICA occlusions). Similarly, we assign a weakly informative prior distribution for both π_S^E and π_S^M , that is, a beta distribution with two shape parameters at 0.35 and 0.65, which centers at 0.35 with an effective sample size of 1.

The rule of step 1 for sICH in this group can be pre-determined in the following table.

Find your number of **endovascular patients with Extracranial ICA occlusions** in the left-side column (we provide the table up to 100 patients, but if we enroll more than 100 patients in this group, we will run the algorithm and identify the # of sICHs which will trigger the rule). The step 1 for sICH will be triggered if the number of sICHs is in the range in the right-side column (the range is inclusive):

# of patients with extracranial ICA occlusions	# of sICHs
20	11-20
30	16-30
40	20-40
50	24-50
60	28-60
70	32-70
80	36-80
90	40-90
100	44-100

For mortality,

- 1) **Step 1 for mortality:** check whether the posterior probability that the rate of mortality at Day 90 in one of the endovascular group is $> 40\%$ exceeds the cut-off 0.95. That is, check whether $\Pr\{\pi_m^E > 0.40 \mid \text{data}\} > 0.95$, where the mortality rate in this endovascular group is denoted as π_m^E .

In the event that Step 1 for mortality in one of the endovascular group is triggered, step 2 for mortality in this group will be executed. Otherwise, continue the trial.

- 2) **Step 2 for mortality:** if Step 1 for mortality in one of the endovascular group is triggered, check whether the posterior probability that the mortality rate in this endovascular group is higher than the corresponding medical management by 10% exceeds the cut-off 0.95. That is, check whether $\Pr\{\pi_m^E > \pi_m^M + 10\% \mid \text{data}\} > 0.95$, where the mortality rate in the corresponding medical management group is denoted as π_m^M .

In the event that Step 2 for mortality in one of the endovascular group is triggered, patient enrollment will be placed on hold and a meeting of the DSMB will be conducted to discuss the events and make a determination on the continuation of the trial.

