SELECT 2 will have an independent Data and Safety Monitoring Board (DSMB) to oversee study safety. Patients in both study arms will be assessed for the incidence of stroke-related mortality at 90 days, the incidence of symptomatic intracranial hemorrhage per SITS-MOST definition within 24 hours after randomization (defined as a ≥ 4 point worsening of immediate pre-deterioration NIHSS neurological status vs. post deterioration and associated with brain hemorrhage), and the incidence of significant neurologic deterioration prior to discharge (defined as ≥ 4 point worsening of the immediate pre-deterioration NIHSS neurological status vs. post deterioration and not attributed to sedation). Patients in both arms will also be assessed for intra-procedural complications including intra-procedural mortality, vessel perforation, arterial dissection, access site complication requiring surgical repair or blood

transfusion, embolization and device failure. SAEs will be reported within 24 hours of awareness of the event.

The DSMB will meet in person or by teleconference, on a semi-annual basis, to monitor the cumulative safety data during participant follow-up. In no instance will more than 12 months elapse between DSMB reviews of cumulative safety data after the first participant has been enrolled. The DSMB will monitor the study according to the guidelines specified in the study protocol and the operating procedures established at the initial meeting unless the DSMB determines during the course of the trial that modification of the guidelines is in the best interest of the study and its participants. The DSMB charter can be found as an attachment to the protocol.

16. Independent Medical Safety Monitor

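### The secondary safety outcome of neurological worsening is restricted by an undefined cause clause that can drop procedure-caused events, which arise almost only in the thrombectomy arm

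*Combined protocol and SAP*

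**What the plan says.** Section 3.7.1.2 lists neurological worsening among the secondary safety outcomes. It requires a rise of at least 4 NIHSS points and restricts it to an "increase on the NIHSS score within 24 hours due to the stroke itself". The section does not say what counts as the stroke itself or who decides.

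Section 6.1 (Secondary analyses) names neurological worsening among the binary outcomes for which a chi-square or Fisher test "where appropriate will be used to compare the incidence between two treatment groups", with adjusted logistic regression in addition. It neither repeats nor relaxes the cause restriction.

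Two other sections describe the same kind of event differently:

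- Section 3.10: "If clinical worsening (defined as a ≥ 4 point increase on the NIHSS score) occurs prior to discharge", imaging follows, and "Neurological worsening is a reportable adverse event". There is no restriction by cause.
- Section 15 (DSMB): a worsening of at least 4 points before discharge, measured against the status just before the deterioration, "vs. post deterioration and not attributed to sedation". Sedation is the only excluded cause.

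Mortality has a smaller mismatch. Section 15 has the DSMB follow "the incidence of stroke-related mortality at 90 days", while the section 10 rule uses "the rate of mortality at Day 90 in one of the endovascular group", with no limit by cause.

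**The concern.** A between-arm safety endpoint should count the harm that the intervention can do. Section 8 lists complications of thrombectomy that could raise the NIHSS, including new arterial clot, embolism, arterial rupture and loss of blood flow to the brain. On a plain reading, worsening from these is caused by the procedure and not by the presenting stroke, so it need not be counted. Only one arm is assigned the procedure (section 3.3, 1:1 allocation).

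The trial is open-label (section 3.1). Blinding is stated for the mRS and Neuro-QoL assessors and for the core laboratory, but not for the 24-hour NIHSS or for any judgement of cause. Calling an event procedural largely reveals the arm in any case.

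At stake is one published safety comparison. It could favour EVT because part of the EVT harm was classified out of it, and the same patient could be a case for the DSMB and a non-case in the trial report.

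**Working it through.** The plan states no rate, power or sample size for this endpoint, so there is no design figure to reproduce. The check is textual, followed by an illustration.

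**Definitions side by side**

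| Section | Threshold | Window | Cause |
|---|---|---|---|
| 3.7.1.2 | at least 4 points | 24 hours | the stroke itself only |
| 3.10 | at least 4 points | before discharge | any |
| 15 | at least 4 points | before discharge | any except sedation |
| 6.1 | not restated | not restated | not restated |

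No section lifts the restriction in 3.7.1.2. A procedural embolus that raises the NIHSS by 4 points at 20 hours, without hemorrhage, is a case under 3.10 and 15. Under 3.7.1.2 it may or may not be one, depending on how an undefined phrase is read.

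**Illustration: inputs**

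- n = 280 per arm. Section 10 gives 280 as the maximum in the EVT group, and allocation is 1:1.
- True all-cause worsening rate p, assumed equal in both arms: 8% and 28%, the rates 14/173 and 5/18 that section 1.2 reports in thrombectomy patients of the prior cohort, and 15% as an assumed middle value.
- Share f of EVT events classed as procedural and dropped: 10%, 20%, 30%. This is an assumption; the documents give no figure.
- Two-sided 5% test of two proportions, normal approximation (assumed).

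**Formulas**

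- Apparent EVT rate: q = p(1 − f). Events dropped: 280·p·f.
- SE under the null: s0 = √[2m(1 − m)/280], with m = (p + q)/2.
- SE under the alternative: s1 = √{[p(1 − p) + q(1 − q)]/280}.
- Chance of a significant result favouring EVT: Φ{[(p − q) − 1.96·s0]/s1}.

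Worked case, p = 0.28 and f = 0.30: q = 0.196, p − q = 0.084, m = 0.238, s0 = 0.0360, s1 = 0.0358. Then (0.084 − 1.96 × 0.0360)/0.0358 ≈ 0.38, and Φ gives about 65%.

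| True rate p | f | Apparent EVT rate | Events dropped of 280 | Chance of significant EVT advantage |
|---|---|---|---|---|
| 8% | 10% | 7.2% | 2.2 | 5% |
| 8% | 20% | 6.4% | 4.5 | 11% |
| 8% | 30% | 5.6% | 6.7 | 20% |
| 15% | 10% | 13.5% | 4.2 | 7% |
| 15% | 20% | 12.0% | 8.4 | 18% |
| 15% | 30% | 10.5% | 12.6 | 36% |
| 28% | 10% | 25.2% | 7.8 | 11% |
| 28% | 20% | 22.4% | 15.7 | 33% |
| 28% | 30% | 19.6% | 23.5 | 65% |

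With nothing dropped, the chance is 2.5%.

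**The reverse case.** Suppose EVT truly adds 10 points of worsening, all procedural and all excluded. An all-cause count would detect this with 94%, 84% or 71% power at control rates of 8%, 15% or 28%. Under the restricted definition the two arms look equal, and only the 2.5% chance level in that direction remains.

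**The case against.** Several objections have force.

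- *The clause is not one-sided as a whole.* A reader might infer that it removes events only from the EVT arm. It does not: systemic illness, drug reactions and other non-stroke causes drop from both arms, and medical-arm patients may receive thrombolysis. Only the procedural part is one-sided, and crossovers soften even that.
- *Exclusion of procedural events is an inference.* The text does not name them, and section 8 lists stroke itself as a complication of the procedure. A site could count a procedural embolus as stroke. That leaves the endpoint undefined, which is still a defect because sites can classify the same event differently.
- *Procedural harm is not hidden from the trial.* Symptomatic hemorrhage, mortality, vascular injury and access-site events are separate outcomes. The DSMB sees intra-procedural complications, and section 3.10 makes worsening from any cause reportable. This stands, but it does not repair this comparison: an embolus that causes a 4-point rise without hemorrhage or death may appear in no other listed secondary safety outcome.
- *Unblinded site attribution is not stated.* Section 18 has the investigator grade how adverse events relate to device or procedure, which makes site attribution plausible, but no one is named for this endpoint. The synopsis calls the trial assessor-blinded without extending that to cause.
- *The size rests on assumption.* The 28% is 5 of 18 patients. The 8% comes from patients with favorable CT and a core below 50 cc, a profile this trial excludes. Equal all-cause rates with some EVT events procedural also mean that EVT truly lowers stroke-caused worsening, so the difference is real for the endpoint as worded and misleading only if read as overall safety.
- *Weight.* Section 6.1 calls the secondary-outcome analyses exploratory, and the synopsis omits this outcome from its safety list.

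**Conclusion.** The point holds in limited form. The endpoint in section 3.7.1.2 carries an undefined cause restriction, has no specified blinded adjudication, and conflicts with sections 3.10 and 15 on cause and window. Its procedural part can tilt one exploratory between-arm comparison toward EVT. The direction follows from the design; the size is not known from the documents. The range of about 5% to 65%, against 2.5%, depends on 280 per arm, equal true rates of 8% to 28% and an assumed dropped share of 10% to 30%.

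Two stronger readings are not supported. One is that the trial's safety conclusion as a whole is biased: the primary analysis counts every death as mRS 6, and the section 10 rules use hemorrhage and mortality, not this endpoint. The other is that deaths from procedural causes are missed: sections 3.7.1.2, 6.1 and 10 all use mortality without a cause limit, so the section 15 phrase is a wording mismatch only.

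**What to change.** 1. In section 3.7.1.2, delete the cause clause. Make the between-arm endpoint an NIHSS increase of at least 4 points within 24 hours from any cause, in both arms, and cite that definition in section 6.1.
2. Report presumed cause (index stroke, hemorrhage, procedure, sedation, other) only as a descriptive breakdown. If a sedation exclusion is wanted, make it a sensitivity analysis: section 3.5 places sedation and anesthesia within the thrombectomy procedure, so excluding it in the main analysis would again fall mainly on EVT.
3. Reconcile sections 3.10 and 15 with this definition, for example by labelling the before-discharge version as a separate monitoring measure.
4. In section 15, align the mortality wording with the unrestricted mortality in sections 3.7.1.2, 6.1 and 10.

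This is a wording amendment. The NIHSS at baseline and 24 hours, worsening events and deaths are already collected, so no new data are needed. The cost is that the reported EVT worsening rate may be somewhat higher, and the endpoint will include some non-stroke worsening in both arms.
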